13 PROTOCOL AMENDMENT HISTORY

The table below is intended to capture changes of IRB-approved versions of the protocol, including a description of the change and rationale. A Summary of Changes table for the current amendment is located in [Appendix 1](#).

Summary of Changes in IGHID 12107 Protocol Version 3.0

Section	Summary of changes and rationale
Section 1.1	Description of Sites Enrolling Participants Clarified Duke is also a study site.
Section 1.1 Section 10.5	Description of Study Intervention Clarified vaccination that a maximum of two participants per week will initiate study treatment at Day 0.
Section 1.1 Section 10.5	Participant Study Duration Corrected duration of participation to be approximately 36 weeks (9 months).
Section 2.2.2, Section 6.1.1	C1-C62 Manufacturer Updated the name of C1 and C62 manufacturer from Advent Srl to Advaxia Biologics Srl per Clarification Memo #1 dated February 17, 2023
Section 2.3.1	Known Potential Risks of C1 and C62 Vaccines Updated potential risks to include transient lymphopenia as reported in C1 IB v4 dated 09-Dec-2022 and C62 IB v3 dated 09-Dec-2022
Section 5.1, Section 5.2	Inclusion and Exclusion Criteria Adjusted inclusion and exclusion timelines for IC #13 and #23 as well as EC #3, #5, #6, #8, #10, #12, #13, #14, #16, and #18. Adjusted IC #26 to indicated Magnesium must be > LLN. Clarified which investigational ART is allowed in EC #13.
Section 6.5.2	Prohibited Medications Removed conflicting information regarding allowable window for Mpox vaccination. Adjusted prohibited medication windows for vaccine to align with eligibility criteria. Clarified allowed investigational ART.
Section 8.1.2, Appendix 2	Visit windows Clarified visit windows for telephone call visits (D2, D5, D10, D18, D22, and D30) per Clarification Memo #1 dated February 17, 2023
Section 8.1.3	Medical History Clarified medical history to include significant medical history condition in noted in medical records.

Section	Summary of changes and rationale
Section 8.1.5	Clinical Assessments Clarified vital sign measurements on vaccination days. Clarified post-vaccine assessment.
Section 8.2.14	Laboratory Evaluations Clarified Hepatitis C screening requirements.
Section 8.3, Section 8.4, Section 9.1, Section 9.3, Section 9.4, Section 9.5	Adverse Event Reporting Created Table 21 to summarize adverse event reporting requirements and timelines for Grade 3 or 4 AEs, hypersensitivity or allergic reactions, SAEs, and AESIs. Removed redundant reporting requirements consolidated in Table 21. Adjusted reporting timelines for UNC IRB and FDA in alignment with agency policies.
Section 9.1.1 Section 9.1.2 Section 9.3.1	Adverse Event Toxicity Management Clarified Grade 1 and Grade 2 toxicity management for events related and unrelated to study treatment. Harmonized Grade 3 and Grade 4 AE toxicity management for AEs in Section 9.1.2 and solicited AEs (local or systemic reactions) in Section 9.3.1. Added note to reference Table 21 (AESI reporting) for Grade 3 or greater injection site reactions.
Section 8.4.1	Relationship to Study Intervention Removed instruction to assess causality separately for each study product.
Section 8.4.2	Time Period and Frequency for Event Assessment and Follow-Up Clarified solicited AEs will be followed through 28 days following each dose of study product. Removed references to Day 196.
Section 9.2.3	Delayed Dose Added reference to Section 9.1.2 for additional instructions regarding delayed booster dose in the event of a prior Grade 3 or 4 AE.
Section 11.4	Table 22 Adjusted table numbering after adding Table 21.

Appendix 2 Assessment for Post C62 and C1C62 Vaccine Adverse Reactions

I. Telephone Assessment Schedule

	Day 2	Day 5	Day 10	Day 18	Day 22
Visit Window		± 1 D	± 1 D	± 1 D	± 1 D
Review Symptom Check List for Post Vaccine Local and Systemic Adverse Reactions	X				
Review Symptom Check List for Post vaccine for development of symptoms associated with clotting disorder	X	X	X	X	X

II. Telephone Assessment for Local and Systemic Reactions (Reference Participant Symptom Diary)

1. Review Solicited AE assessment diary on the phone with the participant.
 - a. Observation of solicited AEs?
 - Systemic solicited AEs include increased body temperature, malaise, fatigue, myalgia, arthralgia, headache, nausea, and feverishness.
 - Local solicited AEs include erythema, swelling, pain, pruritus, and warmth at infusion site.
 - b. Observation of other signs/symptoms

III. Telephone Assessment for Development of Symptoms Associated with Clotting Disorder

1. Assess for the following signs and symptoms
 - a. Shortness of breath
 - b. Chest pain
 - c. Blurred vision or other vision changes
 - d. Swelling, pain or erythema in a limb
 - e. Severe or persistent abdominal pain
 - f. Nausea or vomiting
 - g. Dizziness
 - h. Mental status changes
 - i. Seizure
 - j. Severe or persistent headaches
 - k. Easy bruising and/or bleeding
 - l. Microhemorrhage beside the site of vaccination
 - m. Change in gait; problem with walking, balance or coordination
 - n. Weakness
 - o. Facial weakness
 - p. Numbness or tingling
 - q. Difficulty swallowing or slurring of your speech

Those vaccinated should be instructed to contact study staff immediately for clinical evaluation. If symptoms develop after clinical hours or on the weekend the participant should seek immediate medical attention if they develop any of the above.

Appendix 3 SARS-CoV-2 Pandemic Considerations

Sites should follow local guidelines regarding management of participants during periods of SARS-CoV-2 activity (or other public health emergencies), and all applicable DAIDS guidelines.

Participants diagnosed with or suspected of having SARS-CoV-2 infection

Participants with suspected SARS-CoV-2 infection should be offered testing using locally available, FDA-approved or FDA-EUA assays. Participants who become infected with SARS-CoV-2 may remain on study. Sites should follow local guidelines for management of participants in consultation with primary care providers, local specialists, and the protocol team.

Screening and Enrollment

Participants acquiring SARS-CoV-2 during the screening window may complete screening/enrollment, but no study visits should occur while the participant is deemed to be infectious using local guidelines. Screening and enrollment periods can be extended to allow for recovery. However, all entry criteria must be met as described in the protocol. The participant may be required to repeat screening labs and evaluations at a later time point, based on time of initial screening evaluations and recovery from illness, per site investigator discretion.

Intervention Period (Day 0 through Day 35)

Participants acquiring SARS-CoV-2 during study intervention period should not return for study visits until the participant is deemed to be no longer infectious. Participants should be followed using remote visits (e.g., telephone or video) at least weekly to follow the clinical course of disease and to monitor any ongoing AEs. No study treatment should be administered while the infection is thought to be ongoing. This may lead to missing the Day 28 vaccine, in this scenario the participant can receive the booster dose preferably within the 30 days after the Day 28 visit, but can be extended out 60 days, if needed.

Immunogenicity Follow up Period (Day 42 through Day 196)

Participants with suspected SARS-CoV-2 should not return for study visits until the participant is deemed no longer infectious. Participant will be asked to complete the post vaccine leukapheresis procedure when they are recovered from their illness per site investigator discretion. Participants should be followed using remote visits (e.g., telephone or video) at least weekly to follow the clinical course of disease and to monitor any ongoing AEs.

[figure not shown]
SARS-CoV-2 vaccination

Potential IGHID 12107 participants who are participating in a clinical trial with an acceptable experimental SARS-CoV-2 vaccine or who have been vaccinated with an acceptable SARS-CoV-2 vaccine are able to screen after 14 days since receiving the final dose of vaccine. Receipt of licensed SARS-CoV-2 vaccine is encouraged. Participants are allowed to co-enroll in clinical trials of acceptable investigational SARS-CoV-2 agent per PI approval and provided that limits for blood collection volumes can be maintained and vaccination follows eligibility criteria in regards to timing of vaccination.

[figure not shown]
Conduct of visits and assessments of study endpoints during periods of restricted travel or in-person visits

If in-person visits are restricted at the CRS, or if the site investigator feels that in-person visits pose a risk to the participant that alters the overall risk-benefit ratio, then reasonable efforts should be made to conduct study assessments remotely. Sites should follow FDA guidance (<https://www.fda.gov/media/136238/download> or use the more recent FDA updates) for conducting assessments of study endpoints during a public health emergency. Sites can obtain study-required plasma HIV-1 levels and safety laboratories through alternative sites such as a commercial laboratory near the participant's home. The decision to do the test at a commercial laboratory is made by the site based on the local situation. The site should take into account any change in blood volume required based on the laboratory selected.

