NOTE: For female participants receiving ritonavir or cobicistat, estrogen-based contraceptives are not reliable and an alternative method should be suggested.

21. Men and women not of reproductive potential are eligible without requiring the use of contraceptives. Acceptable documentation detailing sterilization and menopause are specified below.

NOTE: Men who have sex with men only will not be required to use contraception.

NOTE: Women who have sex with women only will not be required to use contraception.

NOTE: Written/oral documentation communicated by clinician/clinician's staff of one of the following:

- a. Physician report/letter
- b. Operative report or other source documentation in the patient record (a laboratory report of azoospermia is required to document successful vasectomy)
- c. Discharge summary
- d. Follicle stimulating hormone-release factor (FSH) measurement elevated into the menopausal range as established by the reporting laboratory

22. Agrees not to enroll on another study of an investigational agent during the study period, defined as any unlicensed investigational drug not yet approved for use in humans.
23. Willingness to defer routine vaccination, including influenza, from 14 days prior to enrollment through Day 56 of the study.

NOTE: Individuals who require vaccination will delay enrollment until 14 days after vaccination.

24. Agrees to refrain from blood donation during the course of the study.
25. Participants with Type 2 diabetes must have a hemoglobin A1C <8 within 12 months prior to screening.
26. Adequate organ function as indicated by the laboratory values provided in Table 16.

Table 16 Adequate Organ Function Values for Inclusion

System	Laboratory Value
Hematological	
Absolute neutrophil count	$\geq 1,000 / \text{mcL}$
Platelets	$\geq 150,000 / \text{mcL}$
Hemoglobin	$\geq 12 \text{ g/dL}$ (male) and $\geq 11.5 \text{ g/dL}$ (females)
Coagulation	
Prothrombin Time or INR	$<1.1 \times \text{ULN}$
Chemistry	
Serum potassium levels	WNL
Serum magnesium levels	$>\text{LLN}^1$
Glucose	Screening serum glucose \leq Grade 1 (fasting or non-fasting)
Renal	
Creatinine clearance determined by the 2021 CKD-Epi equation found at: https://www.mdcalc.com/calc/3939/ckd-epi-equations-glomerular-filtration-rate-gfr	eGFR $> 60 \text{ mL/min}$
Hepatic	

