5.2 Exclusion Criteria

1. Women of childbearing age/potential who are breast feeding, pregnant, or planning pregnancy from enrollment to 4 months after the last vaccination.
2. Untreated syphilis infection defined as a positive rapid plasma reagin (RPR) without clear documentation of treatment.

NOTE: Potential participants may rescreen with documentation of adequate treatment.
Participants reporting symptoms consistent with syphilis infection between the screening visit

and the vaccination visit should be assessed to determine the need for repeat testing prior to vaccination.

3. Current treatment for HCV or HCV treatment within 6 months prior to enrollment.
4. HIV RNA ≥ 150 copies/mL in the 6 months prior to screening.
5. Received any infusion blood product or hematopoietic growth factors within 6 months prior to enrollment.

NOTE: receipt of COVID convalescent plasma ≥ 90 days prior to enrollment is not exclusionary.

6. Use of any of the following agents within 90 days prior to enrollment: immunomodulatory, cytokine, or growth stimulating factors such as systemic cytotoxic chemotherapy or immune globulin.
7. Intent to use immunomodulatory treatment during the study.
8. Use of systemic corticosteroids or topical steroids over a total area exceeding 225 cm² within 30 days prior to enrollment, or anticipated need for periodic use of systemic corticosteroids during the study.

NOTE: Participants receiving stable physiologic doses of glucocorticoids, defined as the equivalent of prednisone ≤ 10 mg/day, will not be excluded. Participants receiving inhaled, intranasal, topical (as defined), intermittent intra-articular corticosteroids, or topical imiquimod will not be excluded.

NOTE: Concomitant use of oral/systemic /intra-articular/inhaled/intranasal corticosteroids is prohibited for participants receiving ritonavir or cobicistat.

9. Use of any investigational HIV vaccine or HIV immunotherapy.

NOTE: Exceptions allowed per PI review and approval.

10. Any experimental non-HIV vaccination within the 6 months prior to enrollment.

NOTE: receipt of FDA or EUA approved or licensed COVID-19 vaccines is not exclusionary if ≥ 14 days prior to enrollment on a case by case review by PI or designee.

11. Prior receipt of any adenovirus Group E-vectored vaccines including those for COVID-19 (i.e. AZD1222/AstraZeneca).

NOTE: Prior immunization with smallpox vaccine is not exclusionary.

NOTE: Janssen Ad26COVS1 COVID-19 vaccine is not exclusionary.

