5.4.1 Co-Enrollment Guidelines

Co-enrollment on other studies will be addressed on a case-by-case basis with the study team. Due to the potential interference with monitoring for the effects of this study's treatments, participants will not be able to participate on other studies that provide medications, with the exception of Phase 2 or greater ARV studies.

Co-enrollment in the ACTG 5332 REPRIEVE study (NCT023442900) using FDA approved pitavastatin is permitted provided the participant has taken the study provided medication ≥ 4 months.

Although not a study, some FDA or EUA sanctioned COVID-19 treatments and vaccines are permitted (see eligibility criteria) but must be addressed on a case-by-case basis with the study team.

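### Appendix 3 conflicts with Exclusion 10 on the washout for experimental SARS-CoV-2 vaccines, and with Inclusion 22 and Section 5.4.1 on co-enrolment in trials of investigational agents

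*Protocol*

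**What the plan says.** **Appendix 3, paragraph on SARS-CoV-2 vaccination.** Two groups are covered: people in a trial of an experimental SARS-CoV-2 vaccine judged acceptable, and people already given an acceptable vaccine. Both "are able to screen after 14 days since receiving the final dose of vaccine". The paragraph then adds: "Participants are allowed to co-enroll in clinical trials of acceptable investigational SARS-CoV-2 agent per PI approval". Two conditions follow: blood-volume limits must hold, and "vaccination follows eligibility criteria in regards to timing of vaccination". The term acceptable is not defined.

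**Section 5.1, Inclusion 22.** The participant "Agrees not to enroll on another study of an investigational agent during the study period". The criterion defines such an agent as an unlicensed drug not yet approved for human use.

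**Section 5.2, Exclusion 10.** This bars "Any experimental non-HIV vaccination within the 6 months prior to enrollment". Its note says that "receipt of FDA or EUA approved or licensed COVID-19 vaccines is not exclusionary" when given at least 14 days before enrolment, reviewed case by case.

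**Section 5.4.1.** Co-enrolment is decided case by case, with a limit and a reason: "Due to the potential interference with monitoring for the effects of this study's treatments, participants will not be able to participate on other studies that" supply medications. The exceptions are antiretroviral studies of Phase 2 or later and a named pitavastatin study. Its COVID-19 allowance covers products sanctioned by the FDA or under an EUA.

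**The concern.** Site staff who follow Appendix 3 can screen, and later co-enrol, people whom the numbered criteria exclude. Staff who follow Sections 5.1, 5.2 and 5.4.1 would turn the same people away. Section 7.2.4 lists no longer meeting eligibility as a ground for withdrawal, so a participant who co-enrols under the appendix could be withdrawn under the body of the protocol.

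The trial has 18 participants, and its primary endpoint is a Grade 3 or higher event judged possibly or definitely related to study treatment through Day 56. Section 8.4.1.2 bases that judgement on timing, alternative cause and biological plausibility. A second investigational product, perhaps given blinded, complicates all three. Section 5.4.1 gives this kind of interference as its reason for restricting co-enrolment.

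**Working it through.** **1. Washout.**

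| Rule | Product | Interval | Counted back from |
|---|---|---|---|
| Appendix 3 | experimental SARS-CoV-2 vaccine | 14 days | screening |
| Exclusion 10 | experimental non-HIV vaccine | 6 months | enrolment |
| Exclusion 10, note | approved, EUA or licensed COVID-19 vaccine | 14 days | enrolment |

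The two 14-day rules count from different visits, so both must be put on the enrolment date. Section 5.3 allows screening up to 60 days before enrolment. For someone who screens as soon as Appendix 3 permits, the longest ordinary interval from last dose to enrolment is 14 + 60 = 74 days. Six months is 365.25 / 2 ≈ 183 days. The shortfall is 183 − 74 = 109 days, so the ordinary screening window cannot reconcile the two rules.

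**2. Co-enrolment.** Three questions decide whether the Appendix 3 conditions remove the conflict.

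- Do they address Inclusion 22? No. That criterion has no waiver by the principal investigator. Exclusion 9 has an explicit one, so the protocol states such exceptions where it wants them.
- Do they reach non-vaccine agents? No. The timing condition concerns vaccination only.
- Do they modify the 14-day screening rule? No. That rule stands in a separate sentence.

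The conflict is sharpest for an unlicensed agent. If the other trial uses a licensed drug, Inclusion 22 does not apply, but the medication-study limit in Section 5.4.1 still does.

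**3. Consequence for the primary endpoint.** The plan's one-sided 95% exact upper limits reproduce:

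- 0 of 8: 1 − 0.05^(1/8) = 31.2% (stated 31%).
- 1 of 8: solving (1−p)^8 + 8p(1−p)^7 = 0.05 gives p = 47.1% (stated 47%).

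The step from 31% to 47% follows from any one additional event in an arm of 8. It shows how sensitive the endpoint is to one relatedness call. It does not measure this defect.

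The documents give no rate for extraneous events, so the following is an assumption. Take 2 co-enrolled participants, each with a 5% to 20% chance of a Grade 3 or higher event from another cause that is judged possibly related:

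- At least one such event: 1 − 0.95² = 9.8% to 1 − 0.80² = 36%.
- Both, which alone would trigger the Section 11.5.1 pause: 0.05² = 0.3% to 0.20² = 4%.

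If nobody co-enrols, both probabilities are zero.

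**The case against.** The best answer to this point is that Appendix 3 defers to the main criteria. It ties vaccination timing to them, and elsewhere it says "all entry criteria must be met as described in the protocol". For vaccine trials the timing condition can fairly be read as importing Exclusion 10 and the COVID-19 vaccine ban through Day 56 in Section 6.5.2. That stands for vaccine timing during co-enrolment. It does not settle Inclusion 22, non-vaccine agents or the 14-day sentence, and the sentence on entry criteria belongs to the paragraph on infection acquired during screening.

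It can be added that co-enrolment needs the investigator's approval, that Section 5.4.1 is a case-by-case rule and not a total ban, and that Appendix 3 speaks of screening, not enrolment. All three are correct. The first two limit how often the problem would arise, and the third is allowed for in the 74-day figure.

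Some stronger readings are tempting but not supported:

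- *Primary events become unattributable.* Section 8.4.1.2 counts an event as possibly related even when another cause exists, and an unblinded monitoring committee reviews relatedness at a safety pause. A rule for attribution therefore remains.
- *Exclusion 13 also forbids co-enrolment.* It covers investigational treatment before enrolment. Its note considers co-enrolment in IND studies of FDA-approved drugs case by case.
- *An undisclosed Group E adenovirus vector would blunt the prime.* Section 2.2.5.3 says more data are needed within a phylogenetic group. It reports that sera from ChAd63 recipients did not neutralise ChAdOx1, with no data on immune responses. Exclusion 11 bars such vectors in any case.
- *The washouts are 14 days against about 180.* That comparison mixes the screening and enrolment dates.

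**Conclusion.** The inconsistency is in the current text and has two parts. For experimental SARS-CoV-2 vaccines, screening at the Appendix 3 minimum leads to enrolment at most 74 days after the last dose under the ordinary window, against about 183 days in Exclusion 10. For co-enrolment, Appendix 3 permits what Inclusion 22 bars for unlicensed agents and what Section 5.4.1 bars where the other study supplies medication outside its named exceptions. Nothing states which text prevails, and the January 2024 clarification memo does not take it up.

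The effect on the trial is conditional. Relatedness would be confounded for each co-enrolled participant. Because possibly related events count, the likely direction is more primary events, a higher upper limit and an easier safety pause. The size cannot be derived from the documents, which do not say whether or how many participants would co-enrol. The 74-day figure assumes screening at day 14 and no extension of the screening period. Appendix 3 allows extension for recovery from SARS-CoV-2 infection.

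**What to change.** Reconcile the Appendix 3 vaccination paragraph with the main criteria:

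- Limit the 14-day allowance to approved, EUA or licensed COVID-19 vaccines, counted to enrolment as in Exclusion 10, and refer experimental vaccines to Exclusions 10 and 11.
- Remove the co-enrolment sentence, or make it expressly subject to Inclusion 22 and Section 5.4.1.

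If the sponsor does intend the Appendix 3 exceptions, write them into Inclusion 22, Exclusion 10 and Section 5.4.1, so that one rule applies wherever staff look.

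The first route costs an edit to one appendix paragraph, and a few candidates in SARS-CoV-2 trials wait or are not enrolled. The second costs edits in three places and accepts confounded attribution for those participants.

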Appendix 4 Neurology Testing

Appendix 5 Diagnosis and Management

Appendix 6 MedDRA Preferred Terms (PTs) for TTS

I. MedDRA PTs for large vessel thrombosis and embolism in unusual locations

Aortic embolus, aortic thrombosis, aseptic cavernous sinus thrombosis, brain stem embolism, brain stem thrombosis, carotid arterial embolus, carotid artery thrombosis, cavernous sinus thrombosis, cerebral artery thrombosis, cerebral venous sinus thrombosis, cerebral venous thrombosis, superior sagittal sinus thrombosis, transverse sinus thrombosis, mesenteric artery embolism, mesenteric artery thrombosis, mesenteric vein thrombosis, splenic artery thrombosis, splenic embolism, splenic thrombosis, thrombosis mesenteric vessel, visceral venous thrombosis, hepatic artery embolism, hepatic artery thrombosis, hepatic vein embolism, hepatic vein thrombosis, portal vein embolism, portal vein thrombosis, portosplenomesenteric venous thrombosis, splenic vein thrombosis, spontaneous heparin-induced thrombocytopenia syndrome, femoral artery embolism, iliac artery embolism, jugular vein embolism, jugular vein thrombosis, subclavian artery embolism, subclavian vein thrombosis, obstetrical pulmonary embolism, pulmonary artery thrombosis, pulmonary thrombosis, pulmonary venous thrombosis, renal artery thrombosis, renal embolism, renal vein embolism, renal vein thrombosis, brachiocephalic vein thrombosis, vena cava embolism, vena cava thrombosis, truncus coeliacus thrombosis

II. MedDRA PTs for more common thrombotic events

Axillary vein thrombosis, deep vein thrombosis, pulmonary embolism

III. MedDRA PTs for thrombocytopenia

Autoimmune heparin-induced thrombocytopenia, Heparin-induced thrombocytopenia, Immune thrombocytopenia, Nonimmune heparin associated thrombocytopenia, Spontaneous heparin-induced thrombocytopenia syndrome, Thrombocytopenia, Thrombocytopenic purpura

IV. Text string for “thrombocytopenia” or “low platelets” in symptom text

IGHID 12107 – THE CM (HIV-CORE 008) STUDY – PROTOCOL VERSION 3.0

CLARIFICATION MEMO

DATE: January 22, 2024

SUBJECT: Clarification Memo #1 for IGHID-12107 Protocol Version 3.0

This clarification memo (CM) does not result in a change in the protocol informed consent document. Each site should file a copy of this CM with the protocol for reference. The protocol clarification contained in this memo should be implemented immediately.

This clarification memo further clarifies adverse events are the defined reactogenicity adverse events beginning within 7-days following vaccination. In addition, it updates Appendix 6, MedDRA Preferred Terms (PTs) for Thrombosis with Thrombocytopenia Syndrome (TTS) events. These updates are inclusive of Coagulopathy PTs from CDC Vaccine Adverse Event Reporting System (VAERS) Standard Operating Procedures for COVID-19 (as of 02Feb2022) and Standardised MedDRA Query (SMQ) for embolic and thrombotic events.

Text noted below with a strikethrough represents deletion; text appearing below in bold represents an addition.

1. Section 4.1, Overall Design, page 46

Safety will be assessed for the duration of the study. ~~Solicited AEs will be recorded for 28 days after each dose of study intervention (through Day 57), and AEs, SAEs, MAAEs, and AESIs will be recorded through the EOS.~~

2. Section 8.1.5.j, Solicited Adverse Events, page 71:

Local and systemic predefined solicited AEs for reactogenicity assessment (Section 8.2.10) will be collected in a Participant Symptom Diary for 7 days following the administration of each dose of study product. ~~In addition, assessments of solicited AEs will occur at study visits through 28 days following administration of each dose of study product.~~

3. Section 8.4.2, Time Period and Frequency for Event Assessment and Follow-Up, page 85:

Solicited AEs will be assessed and recorded for 7-28 days following each dose of study product.

4. Section 10.2, Endpoints, page 101:

Secondary ~~Safety~~ **Effectiveness** Endpoint(s):

- Occurrence of any \geq Grade 1 AE including signs/symptoms, lab toxicities, and/or clinical events, that is possibly or definitely related to study treatment any time from the first day of treatment (D0) through D196 (Week 28).

5. Appendix 6, MedDRA Preferred Terms (PTs) for Thrombosis with Thrombocytopenia Syndrome (TTS) events, page 143:

I. MedDRA PTs for large vessel thrombosis and embolism in unusual locations

Aortic embolus, aortic thrombosis, aseptic cavernous sinus thrombosis, brain stem embolism, brain stem thrombosis, carotid arterial embolus, carotid artery thrombosis, cavernous sinus thrombosis, cerebral artery thrombosis, cerebral venous sinus

thrombosis, cerebral venous thrombosis, superior sagittal sinus thrombosis, transverse sinus thrombosis, mesenteric artery embolism, mesenteric artery thrombosis, mesenteric vein thrombosis, splenic artery thrombosis, splenic embolism, splenic thrombosis, thrombosis mesenteric vessel, visceral venous thrombosis, hepatic artery embolism, hepatic artery thrombosis, hepatic vein embolism, hepatic vein thrombosis, portal vein embolism, portal vein thrombosis, portosplenomesenteric venous thrombosis, splenic vein thrombosis, spontaneous heparin-induced thrombocytopenia syndrome, femoral artery embolism, iliac artery embolism, jugular vein embolism, jugular vein thrombosis, subclavian artery embolism, subclavian vein thrombosis, obstetrical pulmonary embolism, pulmonary artery thrombosis, pulmonary thrombosis, pulmonary venous thrombosis, renal artery thrombosis, renal embolism, renal vein embolism, renal vein thrombosis, brachiocephalic vein thrombosis, vena cava embolism, vena cava thrombosis, truncus coeliacus thrombosis, **embolism venous, intracranial venous sinus thrombosis**

- II. MedDRA PTs for more common thrombotic events
Axillary vein thrombosis, deep vein thrombosis, **disseminated intravascular coagulation**, pulmonary embolism, **thrombosis, venous thrombosis**
- III. MedDRA PTs for thrombocytopenia
Acquired amegakaryocytic thrombocytopenia, Amegakaryocytic thrombocytopenia, Autoimmune heparin-induced thrombocytopenia, Heparin-induced thrombocytopenia, Immune thrombocytopenia, Nonimmune heparin associated thrombocytopenia, Severe fever with thrombocytopenia syndrome, Spontaneous heparin-induced thrombocytopenia syndrome, Thrombocytopenia, Thrombocytopenic purpura, Thrombotic thrombocytopenic purpura
- IV. Text string for
“thrombocytopenia” or “low platelets” in symptom text
- V. **Reference additional PTs included in the Standardised MedDRA Query (SMQ) for Embolic and thrombotic events**
